10.2 Patient Characteristics

Demographics and other baseline characteristics will be carried out on the enrolled population.

10.2.1 Demographic and Other Baseline Characteristics

Table 10.2.1.1 Baseline characteristics: Gender

	S1 (TR)		S2 (RT)		Total	
	N	%	N	%	N	%
Gender						
Male						
Female						

Notes: Percentage is based on number of patients in total and by sequence, when applicable.

S1, Sequence 1; S2, Sequence 2; TR, test-reference; RT, reference-test.

Table 10.2.1.2 Baseline characteristics: Race

	S1 (TR)		S2 (RT)		Total	
	N	%	N	%	N	%
Race						
White						
Black						
Asian						
...						
Other (Specify)						

Notes: Percentage is based on number of patients in total and by sequence, when applicable.

S1, Sequence 1; S2, Sequence 2; TR, test-reference; RT, reference-test.

Table 10.2.1.3 Baseline characteristics: Age

	S1 (TR)		S2 (RT)		Total	
	N	%	N	%	N	%
Age at entry (years)						
N						

Mean, Std., Median, Range

S1, Sequence 1; S2, Sequence 2; TR, test-reference; RT, reference-test.

Table 10.2.1.4 Baseline characteristics: Pregnancy Test

	S1 (TR)		S2 (RT)		Total	
	N	%	N	%	N	%
Pregnancy Test						
Positive						
Negative						
NA (Specify)						

Notes: Percentage is based on number of patients in total and by sequence, when applicable.

S1, Sequence 1; S2, Sequence 2; TR, test-reference; RT, reference-test.

Table 10.2.1.5 Baseline characteristics: Adequate contraception

	S1 (TR)		S2 (RT)		Total	
	N	%	N	%	N	%
Adequate contraception						
Yes						
No						
NA						

Notes: Percentage is based on number of patients in total and by sequence, when applicable.

S1, Sequence 1; S2, Sequence 2; TR, test-reference; RT, reference-test.

10.2.2 Medical History

Listing 10.2.2.1 Ongoing medical history

Sequence	Subject	Description	Onset date

10.2.3 Cancer History

Table 10.2.3.1 First diagnosis: Tumor type

	S1 (TR)		S2 (RT)		Total	
	N	%	N	%	N	%
Tumor Type						
Lung						
Kidney						
Prostate cancer						
...						

Notes: Percentage is based on number of patients in total and by sequence, when applicable.

S1, Sequence 1; S2, Sequence 2; TR, test-reference; RT, reference-test.

Table 10.2.3.2 First diagnosis: Stage at diagnosis

	S1 (TR)		S2 (RT)		Total	
	N	%	N	%	N	%
Stage at Diagnosis						
Early						
Locally advanced						
Metastatic						

Notes: Percentage is based on number of patients in total and by sequence, when applicable.

S1, Sequence 1; S2, Sequence 2; TR, test-reference; RT, reference-test.

Table 10.2.3.3 First diagnosis: Time from first diagnosis to first infusion

	S1 (TR)	S2 (RT)	Total
Time from first diagnosis to first infusion (months) [†]			
N			
Mean, Std., Median, Range			

[†] Time from first diagnosis to first infusion: defined as the date of first infusion minus date of first diagnosis.

S1, Sequence 1; S2, Sequence 2; TR, test-reference; RT, reference-test.

Table 10.2.3.4 Current disease: Time from last PD to first infusion

	S1 (TR)	S2 (RT)	Total
Time from last PD [†] to first infusion (months) [‡]			
N			
Mean, Std., Median, Range			

[†] Last PD will be taken from the Cancer history form

[‡] Time from last PD to first infusion: defined as the date first infusion minus date of last progression before study entry.

S1, Sequence 1; S2, Sequence 2; TR, test-reference; RT, reference-test.

Table 10.2.3.5 Current disease: Sites of disease involvement

	S1 (TR)		S2 (RT)		Total	
	N	%	N	%	N	%
Site of disease involvement						
Lung						
Liver						
Lymph node						
Pleura						
Bone						
...						
Other (Specify)						

Notes: Percentage is based on number of patients in total and by sequence, when applicable.

S1, Sequence 1; S2, Sequence 2; TR, test-reference; RT, reference-test.

Table 10.2.3.6 No. of sites of disease involvement

	S1 (TR)		S2 (RT)		Total	
	N	%	N	%	N	%
No. of sites						
1						
2						
...						
≥ N sites						
Total						

Notes: Percentage is based on number of patients in total and by sequence, when applicable.

S1, Sequence 1; S2, Sequence 2; TR, test-reference; RT, reference-test.

Table 10.2.3.7 Summary statistics: No. of sites of disease involvement

	S1 (TR)	S2 (RT)	Total
No. of sites			
N			
Mean, Std., Median, Range			

S1, Sequence 1; S2, Sequence 2; TR, test-reference; RT, reference-test.

10.2.4 Previous Anticancer Therapy Summary**Table 10.2.4.1 Patients with prior surgery**

	S1 (TR)		S2 (RT)		Total	
	N	%	N	%	N	%
Prior surgery						
Yes						
No						

Notes: Percentage is based on number of patients in total and by sequence, when applicable.

S1, Sequence 1; S2, Sequence 2; TR, test-reference; RT, reference-test.

Table 10.2.4.2 Patients with prior radiotherapy

	S1 (TR)		S2 (RT)		Total	
	N	%	N	%	N	%
Prior radiotherapy						
Yes						
No						

Notes: Percentage is based on number of patients in total and by sequence, when applicable.

S1, Sequence 1; S2, Sequence 2; TR, test-reference; RT, reference-test.

Table 10.2.4.3 Prior anticancer medical therapy for study disease: No. of prior lines

	S1 (TR)		S2 (RT)		Total	
	N	%	N	%	N	%
No. of prior lines						
1 line						
2 lines						
3 lines						
>= 4 lines						

Notes: Percentage is based on number of patients in total and by sequence, when applicable.

S1, Sequence 1; S2, Sequence 2; TR, test-reference; RT, reference-test.

Table 10.2.4.4 Prior anticancer medical therapy for study disease: Summary of prior lines

	S1 (TR)	S2 (RT)	Total
No. of prior lines			
N			
Mean, Std., Median, Range			

S1, Sequence 1; S2, Sequence 2; TR, test-reference; RT, reference-test.

Table 10.2.4.5 Prior anticancer medical therapy for study disease: No. of prior chemotherapy lines

	S1 (TR)		S2 (RT)		Total	
	N	%	N	%	N	%
No. of prior chemotherapy lines						
1 line						
2 lines						
3 lines						
>= 4 lines						

Notes: Percentage is based on number of patients in total and by sequence, when applicable.

S1, Sequence 1; S2, Sequence 2; TR, test-reference; RT, reference-test.

Table 10.2.4.6 Prior anticancer medical therapy for study disease: Summary of prior chemotherapy lines

	S1 (TR)	S2 (RT)	Total
No. of prior chemotherapy lines			
N			
Mean, Std., Median, Range			

S1, Sequence 1; S2, Sequence 2; TR, test-reference; RT, reference-test.

Table 10.2.4.7 Prior anticancer medical therapy for study disease: No. of prior agents

	S1 (TR)		S2 (RT)		Total	
	N	%	N	%	N	%
No. of prior agents						
0 agents						
1 agent						
2 agents						
3 agents						
≥ 4 agents						

Notes: Percentage is based on number of patients in total and by sequence, when applicable.

S1, Sequence 1; S2, Sequence 2; TR, test-reference; RT, reference-test.

Table 10.2.4.8 Prior anticancer medical therapy for study disease: Summary of prior agents

	S1 (TR)	S2 (RT)	Total
No. of prior agents			
N			
Mean, Std., Median, Range			

Table 10.2.4.9 First anticancer medical therapy for study disease: Time to progression of last therapy

Time to progression (months)	S1 (TR)	S2 (TR)	Total
N			
Mean, Std., Median, Range			

10.2.5 Physical Examination, ECOG, Vital Signs, LVEF and ECG

Table 10.2.5.1 Baseline physical examination

Physical examination	S1 (TR)		S2 (RT)		Total	
	N	%	N	%	N	%
Normal						
Abnormal						

Notes: Percentage is based on number of patients in total and by sequence, when applicable.

S1, Sequence 1; S2, Sequence 2; TR, test-reference; RT, reference-test.

Listing 10.2.5.2 Baseline physical examination: abnormalities

Sequence	Subject	Description

Table 10.2.5.3 Baseline physical examination: Weight, height and BSA

	S1 (TR)	S2 (RT)	Total
Weight (kg)			
N			
Mean, Std., Median, Range			
Height (cm)			
N			
Mean, Std., Median, Range			
BSA (m ²)			
N			
Mean, Std., Median, Range			

S1, Sequence 1; S2, Sequence 2; TR, test-reference; RT, reference-test.

Table 10.2.5.4 Baseline physical examination: ECOG Performance Status

ECOG	S1 (TR)		S2 (RT)		Total	
	N	%	N	%	N	%
0						
1						
...						
Total						

Notes: Percentage is based on number of patients in total and by sequence, when applicable.

S1, Sequence 1; S2, Sequence 2; TR, test-reference; RT, reference-test.

Table 10.2.5.5 Baseline characteristics: Vital signs

	S1 (TR)	S2 (RT)	Total
Heart rate (Beats/minute)			
N			
Mean, Std., Median, Range			
Temperature (°C)			
N			
Mean, Std., Median, Range			
Blood pressure systolic (mmHg)			
N			
Mean, Std., Median, Range			
Blood pressure diastolic (mmHg)			
N			
Mean, Std., Median, Range			

S1, Sequence 1; S2, Sequence 2; TR, test-reference; RT, reference-test.

Table 10.2.5.6 Baseline characteristics: ECG[†] pre infusion

	S1 (TR)		S2 (RT)		Total	
	N	%	N	%	N	%
Result						
Normal						
Abnormal						

Notes: Percentage is based on number of patients in total and by sequence, when applicable.

† Worst result of the three ECGs replicates will be used as baseline value.

S1, Sequence 1; S2, Sequence 2; TR, test-reference; RT, reference-test.

Table 10.2.5.7 Baseline characteristics: Pre infusion ECG[†] values

	S1 (TR)		S2 (RT)		Total	
	N	%	N	%	N	%
PR interval (msec)						
N						
Mean, Std., Median, Range						
Heart rate (bpm)						
N						
Mean, Std., Median, Range						
QT interval (msec)						
N						
Mean, Std., Median, Range						
Bazett's corrected QT						
N						
Mean, Std., Median, Range						
Fridericia's corrected QT						
N						
Mean, Std., Median, Range						

† Mean of the three ECGs replicates will be used as baseline value.

S1, Sequence 1; S2, Sequence 2; TR, test-reference; RT, reference-test.

Table 10.2.5.8 Baseline characteristics: Post-infusion ECG[†] values

	S1 (TR)		S2 (RT)		Total	
	N	%	N	%	N	%
PR interval (msec)						
N						
Mean, Std., Median, Range						
Heart rate (bpm)						
N						
Mean, Std., Median, Range						
QT interval (msec)						
N						
Mean, Std., Median, Range						
Bazett's corrected QT						
N						
Mean, Std., Median, Range						
Fridericia's corrected QT						
N						
Mean, Std., Median, Range						

† Mean of the three ECGs replicates will be used as baseline value.

S1, Sequence 1; S2, Sequence 2; TR, test-reference; RT, reference-test.

Listing 10.2.5.9 Patients with abnormal electrocardiogram

Sequence	Subject	ECG no.	Abnormality	PR interval (msec)	Heart rate (bpm)	QT interval (msec)	Bazett's corrected QT

Table 10.2.5.10 Baseline characteristics: LVEF

	S1 (TR)		S2 (RT)		Total	
	N	%	N	%	N	%
Result						
Normal						
Abnormal						

Notes: Percentage is based on number of patients in total and by sequence, when applicable.

S1, Sequence 1; S2, Sequence 2; TR, test-reference; RT, reference-test.

Listing 10.2.5.11 Patients with abnormal LVEF

Sequence	Subject	Result	Method	Value (%)	Lower limit (%)	Abnormalities

Notes: Significant and non-significant abnormalities

Table 10.2.5.12 Baseline characteristics: LVEF value

LVEF (%) by Method	S1 (TR)		S2 (RT)		Total	
	N	%	N	%	N	%
MUGA						
N						
Mean, Std., Median, Range						
ECHO						
N						
Mean, Std., Median, Range						
Both						
N						
Mean, Std., Median, Range						

S1, Sequence 1; S2, Sequence 2; TR, test-reference; RT, reference-test.

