^e ECG should be done in triplicate (at screening, Day 1 and EOT visit) and allow rhythm definition (at least 30 seconds of duration), PR interval and QT interval (raw and corrected by HR using Bazett's formula). On Day 1, 5 minutes before SOI (-25 to -1 min before preinfusion PK samples collection) and 1 hour after EOI (-15 to -1 min before the PK sample collection), both will be done in triplicate.

^f A previous LVEF assessment could be used if was made within 28 days prior to screening and will be repeated if clinically indicated, and EOT.

^g Randomization apply for all patients.

^h Bosentan for self-administration and the patient's diary should be given to the patient on Day -6 with a $-2/+1$ day time window (i.e., from Day -8 to Day -5).

ⁱ Corticosteroids i.v. (according to institutional standard antiemetic doses, minimum dose of 8 mg/day and maximum dose of 20 mg/day of dexamethasone sodium phosphate or equivalent); If feasible, anti-emetic medication and dose administered in Cycle 1 should be maintained in Cycle 2. Serotonin (5-HT₃) antagonists (ondansetron at least 8 mg i.v. and no more than 16 mg of ondansetron) (i.e., 30 \pm 5 minutes before lubrinezdin administration).

^j If patient does not fulfill inclusion criteria (Cycle 1 in TR sequence) in Day 1 assessments and lubrinezdin administration is postponed no more than two days, bosentan should not be discontinued.

Study Period►	Screening (days prior to registration)	Cycle 1												Cycle 2					Cycle 3	End of Treatment	Follow-up AEs
		-6	-5	-4	-3	-2	-1	1*	2	3	5	8	15	1	2	3	5	8	15		
Cycle Day►																					

^k The study center will contact the patients (via telephone or other methods) to remind them or confirm that they have taken the morning and evening dose of bosentan when they are not at the study center.

^l Blood sample for genotyping will be collected at any time during the study but preferably just before infusion start in Cycle 1, only if written IC for the pharmacogenetic sub-study is given.

^m Serial peripheral venous blood samples for determination of lubinectedin (total and unbound), lubinectedin metabolites (i.e., M1 and M4) and bosentan plasma concentrations will be collected at the time points indicated in Section [8.1.1, Table 9](#).

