	
 ♦ Coagulation (INR): 	
Sequence 1 (TR) and Sequence 2 (RT): Repeat on Day 1 of Cycle 1 (prior to lorbinecetin infusion) if more than ten days have passed since the screening assessment. Also repeat if clinically indicated.

	
 ♦ Calculated CLcr: Cockcroft and Gault's formula (Appendix 4).^c 	
Sequence 1 (TR) and Sequence 2 (RT): Cycle 1: Day 8 and Day 15. Also repeat on Day 1 of Cycle 1 (prior to lorbinecetin infusion) if more than ten days have passed since the screening assessment. Cycle 2: Day 1, Day 8 and Day 15. Cycle 3: Day 1. (always prior to lorbinecetin infusion).

3. Pregnancy test	Only applicable to WOCBP. Assessment of β-hCG (in serum).	During the on-treatment period, testing should be done be every cycle (always prior to lorbinecetin infusion). Also repeat on Day 1 of Cycle 1 (prior to lorbinecetin infusion) if more than seven days have passed since the screening assessment.
4. Pharmacokinetics	
 ♦ Cycle 1 and Cycle 2: Eleven blood samples each (before lorbinecetin infusion start, 5 min before end of lorbinecetin infusion and 30 min, 1 hour, 2 hours, 4 hours, 6 hours, 24 hours, 48 hours, 96 hours, 168 hours after the end of lorbinecetin infusion) will be collected for pharmacokinetic analyses (see details in Section 8.1.1). 	
Sequence 1 (TR) and Sequence 2 (RT): Cycle 1 and Cycle 2. PK sampling for bosentan will be done in Cycle 1 for patients assigned to Sequence 1 (TR), and in Cycle 2 for assigned to Sequence 2 (RT). See Table 9.

5. AAG and IL6 collection	One blood sample per cycle.	Sequence 1 (TR) and Sequence 2 (RT): On Day 1 of Cycle 1 and Cycle 2 (always prior to lorbinecetin infusion).
6. Pharmacogenetics (only if written informed consent given)	One blood sample.	Sequence 1 (TR) and Sequence 2 (RT): At any time during the study, but preferably just before lorbinecetin infusion start in Cycle 1.
7. ECG	ECG should be done in triplicate and cardiac rhythm will be identified in ECG intervals of at least 30 seconds of duration, PR interval, QT interval (raw and corrected by HR using Bazett's formula).	Sequence 1 (TR) and Sequence 2 (RT): On Day 1 of Cycle 1 and Cycle 2, 5 minutes before SOI (-25 to -1 min before preinfusion PK samples collection) and 1 hour after EOI (-15 to -1 min before the PK sample collection).

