7.1 Baseline and Demographics

Descriptive statistics will be used to summarize the patients' baseline characteristics

Baseline data such as demographics, cancer history, prior therapy, prior relevant history, signs and symptoms, ECG, LVEF, physical examination, vital signs, laboratory values and concomitant medication, coded according to the World Health Organization (WHO) Anatomical Therapeutic Chemical (ATC) classification system, will be described following standard tables (detailed in Section 10, Appendix I).

Age, baseline weight, height and BSA values will be summarized descriptively. Age categories, sex, race and baseline ECOG PS will be summarized with frequency counts.

For the cancer history, times from initial diagnosis, metastatic disease, from locally advanced disease and from last progression before the study entry will be summarized. These time calculations will be shown in months and summarized descriptively. Histology and characteristics of the disease at study entry will be tabulated.

Previous relevant medical history (other than cancer) will be listed.

A frequency tabulation of the number of patients with the different types of previous surgery, radiotherapy or therapy will be given.

Signs and symptoms will be displayed by tabulation of frequencies according to NCI-CTCAE v.5 toxicity grades. Signs and symptoms will be listed.

In case of pre-treatment characteristics with multiple measurements per subject before the start of treatment (e.g. laboratory assessments or vital signs), the last value prior to or on the first day of treatment will be considered the baseline measurement.

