11.6.2 LVEF and ECG

Listing 11.6.2.1 Patients with abnormal or clinically indicated LVEF during the study

Sequence	Subject	Assessment Date	Abnormality	Specify	Method	LVEF (%)	Lower limit of normality

Sequence	Subject	Assessment Date	Abnormality	Specify	Method	LVEF (%)	Lower limit of normality

Listing 11.6.2.2 Electrocardiogram evolution during the study

Sequence	Subject	% Change [†]					
		ECG parameters*	Cycle 1 Pre infusion	Cycle 1 Post infusion	Cycle 2 Pre infusion	Cycle 2 Post infusion	EOT
		Baseline					
S1 (TR)	...						
S2 (RT)	...						

* PR interval (msec), Heart rate (bpm), QT interval (msec), QRS complex duration, Fridericia corrected QT

† % compared to baseline

‡ Triplicate ECG values obtained at each time point (baseline, Day 1 of Cycle 1 pre-infusion and post-infusion, Day 1 of Cycle 2 pre-infusion and post-infusion and end of treatment) are averaged

S1, Sequence 1; S2, Sequence 2; TR, test-reference; RT, reference-test.

Listing 11.6.2.3 Patients with abnormal or clinically indicated Electrocardiogram during the study

Sequence	Subject	Assessment Date	Result	Specify	PR Interval (msec)	Heart rate (bpm)	QT interval (msec)	Bazett's corrected QT

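### SAP 10.2.5 labels two different Day 1 ECG triplicates as baseline, one of them post-infusion, and the date-only rule in SAP 7.1 does not settle which ECG is the reference

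*SAP*

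**What the plan says.** The protocol's schedule of assessments sets the ECG visits: "ECG should be done in triplicate (at screening, Day 1 and EOT visit". On Day 1 of Cycles 1 and 2 there are two triplicates, one 5 minutes before the infusion starts and one "1 hour after EOI (-15 to -1 min before the PK sample collection" (Protocol 6.4, Table 5).

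SAP 7.1 counts the ECG as baseline data: "Baseline data such as demographics, cancer history, prior therapy, prior relevant history, signs and symptoms, ECG, LVEF". Where a pre-treatment characteristic has several measurements, "the last value prior to or on the first day of treatment will be considered the baseline measurement".

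SAP 10.2.5 then has two tables of ECG values under the baseline heading. Table 10.2.5.7 ("Baseline characteristics: Pre infusion ECG") holds the pre-infusion values and Table 10.2.5.8 the post-infusion values. Both carry the footnote "Mean of the three ECGs replicates will be used as baseline value". No ECG table in that section is labelled as screening.

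Listing 11.6.2.2 gives percentage change from baseline for each patient. Its footnote lists the time points as "Triplicate ECG values obtained at each time point (baseline, Day 1 of Cycle 1 pre-infusion and post-infusion", followed by the Cycle 2 and end-of-treatment triplicates. Baseline is therefore distinct from both Cycle 1 Day 1 triplicates.

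**The concern.** A change from baseline needs one reference value, and to show a drug effect that value should precede the drug. Here two triplicates from the same day are each called the baseline value, and one follows the infusion.

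A date-only rule does no harm for laboratory tests and vital signs, because Protocol 6.4 places those Day 1 assessments before the infusion. The ECG differs: on Day 1 it is scheduled on both sides of the infusion, so the last value of that date is a post-dose value.

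What is at stake is the percentage-change listing for PR, heart rate, QT and corrected QT. With the post-infusion triplicate as reference, an acute effect in Cycle 1 would show as no change after infusion and as an apparent fall before it. The reference could also differ between the two sequences.

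**Working it through.** The plan states no ECG figure to reproduce. The check has two parts: which triplicate each passage selects, and what the choice does to Listing 11.6.2.2.

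**Which triplicate is baseline?** Protocol 5.2 starts treatment at the first dose of bosentan or lurbinectedin.

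| Source | Sequence 1 (TR) | Sequence 2 (RT) |
|---|---|---|
| SAP 7.1, date wording alone, first day = first study drug | Screening (first day is Day -5, bosentan) | Cycle 1 Day 1 post-infusion |
| SAP 7.1, first day = first infusion day | Cycle 1 Day 1 post-infusion | Cycle 1 Day 1 post-infusion |
| Table 10.2.5.7 | Cycle 1 Day 1 pre-infusion, after five days of bosentan | Cycle 1 Day 1 pre-infusion, drug-free |
| Table 10.2.5.8 | Cycle 1 Day 1 post-infusion | Cycle 1 Day 1 post-infusion |
| Listing 11.6.2.2 | Neither Day 1 triplicate; by elimination, screening | Same |

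The entries do not agree. Only screening precedes both drugs in both sequences.

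**What the choice does.** The inputs are assumptions, not document figures: corrected QT of 420 ms at screening, before each infusion and at end of treatment, and an acute post-infusion rise d of 5, 10 or 20 ms in both cycles. The formula is % change = 100 × (value − baseline) / baseline.

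- Baseline = screening (420). Cycle 1 post-infusion change is 100 × d/420: 5/420 = +1.19%, 10/420 = +2.38%, 20/420 = +4.76%. The pre-infusion change is 0.
- Baseline = Cycle 1 post-infusion (420 + d). Cycle 1 post-infusion change is 0 for every d. The pre-infusion change is −100 × d/(420 + d): −5/425 = −1.18%, −10/430 = −2.33%, −20/440 = −4.55%. The Cycle 2 pre-infusion and end-of-treatment columns show the same falls, and Cycle 2 post-infusion shows 0.

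**Is the information lost?** No. Dividing (1 + post-infusion change) by (1 + pre-infusion change) and subtracting 1 returns the acute effect. From the rounded entries above this gives about +1.19%, +2.39% and +4.77%; the small differences from the direct values are rounding.

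**How many patients?** With eight patients randomized 1:1, the first-study-drug reading touches the four in Sequence 2.

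**The case against.** The strongest reply is that the plan, read as a whole, never makes the post-infusion triplicate the reference.

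- The SAP 7.1 rule is framed around "multiple measurements per subject before the start of treatment (e.g. laboratory assessments or vital signs". A value taken after the infusion is not a measurement before treatment starts, and the ECG is not among the examples. This stands in part: it makes the rule ambiguous, so the rule does not plainly call for a post-dose value. The closing date wording still lacks a time condition.
- Listing 11.6.2.2 separates baseline from both Day 1 triplicates, so screening is its natural reading. This stands. It also means the listing disagrees with both footnotes in SAP 10.2.5.
- The footnote to Table 10.2.5.8 repeats that of Table 10.2.5.7 word for word, and may only describe how replicates are averaged. That is plausible, but the table still sits under the baseline heading.
- The effect remains visible elsewhere. Tables 10.2.5.7 and 10.2.5.8 show pre- and post-infusion summaries, and Listing 13.25 gives each ECG. This stands.

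A reader might infer that the plan removes an acute lurbinectedin ECG effect from its change-from-baseline results, or that ECG changes cannot be compared between sequences. The documents do not support either. The first requires the post-infusion triplicate to be the listing's reference, which the listing does not say. The second presupposes a between-sequence comparison of ECG change, and none is planned: the output is a listing by patient, and the model in SAP 11.5 covers adverse events and laboratory abnormalities.

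**Conclusion.** The inconsistency is real and sits in the current SAP text. Two Day 1 triplicates are each called the baseline value, one of them post-infusion; the SAP 7.1 rule has no pre-dose condition; and Listing 11.6.2.2 points to a third ECG.

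The consequence is conditional. Only if the post-infusion triplicate were used as reference would the Cycle 1 post-infusion change be zero by construction in the affected patients. The percentages illustrate the pattern under an assumed QTc and assumed rises; they do not estimate any effect of the drug. A reader might put all eight patients at risk. That needs the first day of treatment to mean the first infusion day, a convention the SAP uses in its baseline laboratory footnotes (10.2.6 to 10.2.8) but does not state for the ECG.

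The ECG is a descriptive safety output, and the primary PK analysis is unaffected. Severity: minor.

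**What to change.** 1. In SAP 7.1 and 10.2.5, define one ECG baseline: the mean of the screening triplicate. It precedes both drugs in both sequences, whereas the Day 1 pre-infusion ECG in Sequence 1 follows five days of bosentan.
2. Retitle Table 10.2.5.8 as Cycle 1 Day 1 post-infusion (on-treatment) values and delete its baseline footnote.
3. Label Tables 10.2.5.6 and 10.2.5.7 as Cycle 1 Day 1 pre-infusion values.
4. State that Listing 11.6.2.2 is computed from the screening baseline.

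A same-day post-minus-pre change for each cycle would be a useful addition, but is optional. The cost is SAP wording and minor programming. Every ECG needed is already scheduled.
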